Appendix 1 Schedule of Assessments (cont.)

-
- ^l Perform Lansky Performance Status for patients < 16 years old and Karnofsky Performance Status for patients ≥ 16 years old.
- ^m Hematology includes WBC count, hemoglobin, platelet count, 3-cell differential count (absolute neutrophils, monocytes, and lymphocytes). Starting with Cycle 8, these assessments should take place every other cycle (e.g., Cycles 8, 10, 12, etc.).
- ⁿ Laboratory tests should be performed ≤ 96 hours prior to Day 1 of each scheduled cycle. Screening labs may be used for Cycle 1, Day 1 hematology, chemistry, and urinalysis if drawn within two weeks of Cycle 1 Day 1.
- ^o Chemistry includes sodium, potassium, magnesium, chloride, bicarbonate, glucose, BUN or urea, creatinine, total protein, albumin, phosphorus, calcium, total bilirubin (if abnormal, fractionate sample for direct and indirect), alkaline phosphatase, ALT, AST, LDH. Starting with Cycle 8, these assessments should take place every other cycle (e.g., Cycles 8, 10, 12, etc.).
- ^p Urinalysis includes specific gravity, glucose, protein, and blood in patients > 3 years of age. Starting with Cycle 4, urinalyses should take place every other cycle (e.g., Cycles 4, 6, 8, etc.). Creatinine clearance should be done as clinically indicated. If radioisotope glomerular filtration rate is routinely performed at the institution to measure patients' creatinine clearance, this test can be used to assess renal function at screening, per the eligibility criteria. Otherwise, serum creatinine is sufficient to document renal function at screening.
- ^q Amylase and lipase testing should be done at screening and then every two cycles (e.g., Cycles 2, 4, 6, etc.).
- ^r Thyroid function testing includes thyroid-stimulating hormone, free T3, and free T4. Thyroid function testing should take place every two cycles (e.g., Cycles 2, 4, 6, etc.).
- ^s Includes hepatitis B surface antigen, hepatitis B surface antibody, total hepatitis B core antibody, hepatitis C antibody, HIV-1, and HIV-2 antibody. If patient is positive for hepatitis B core antibody at screening, a test for hepatitis B virus DNA should be performed prior to Day 1 of Cycle 1. If patient is positive for hepatitis C antibody at screening, a test for hepatitis C virus RNA should be performed prior to Day 1 of Cycle 1.
- ^t Blood samples will be obtained to characterize biomarkers, atezolizumab pharmacokinetics, and ATAs according to the schedule in [Appendix 2](#).
- ^u Collect sample between 90 to 150 days after last dose of study drug.
- ^v The same *imaging technique(s) and procedure(s)* (CT, MRI, FDG-PET, *and/or* MIBG scan) used to assess disease sites at screening should be used throughout the study (e.g., the same contrast protocol for CT scans). To the extent that is feasible, assessments should be performed by the same evaluator to ensure internal consistency across visits. See Section 4.5.5 for detailed information on tumor and response evaluations.
- ^w Tumor assessments must be performed during the last week of Cycles 2, 4, 6, and 8 and every 4th cycle thereafter (i.e., within 7 days prior to Day 1 of the next cycle). At the investigator's discretion, tumor assessments may be repeated at any time if progressive disease is suspected. An objective response should be confirmed by repeat assessments ≥ 4 weeks after initial documentation. Patients who discontinue study drug without progressive disease should continue follow up assessments, including tumor assessments, using the long-term follow up schedule (e.g., every three months for the first 2 years, every 6 months during year 3, etc.) until radiographic documentation of progressive disease, they start another treatment or consent is withdrawn. Patients who continue to receive study drug beyond radiographic progressive disease should continue follow-up assessments until they stop taking study drug.

Appendix 1 Schedule of Assessments (cont.)

- ^x Atezolizumab will be administered by IV infusion every 3 weeks. Patients will be weighed at the beginning of each cycle, and the dose will be adjusted as needed.
- ^y Includes any medication (e.g., prescription drugs, over-the-counter drugs, herbal or homeopathic remedies, nutritional supplements) used by a patient from 7 days prior to screening to the study drug discontinuation visit.
- ^z Only required in children who have been vaccinated.
- ^{aa} Samples should be obtained prior to infusion of the first dose and will be held for possible testing in patients who develop immune-related or inflammatory adverse events during the study. Auto-antibody testing to include at least anti-nuclear antibody, anti-double-stranded DNA, circulating anti-neutrophil cytoplasmic antibody, and perinuclear anti-neutrophil cytoplasmic antibody.
- ^{bb} Patients who are willing to participate must provide separate informed consent for collection of tumor tissue samples for the RCR. Sample collection is not applicable if the site has not been granted approval for RCR sampling.
- ^{cc} Optional RCR tumor tissue samples will be collected prior to drug initiation, 4 weeks after the first dose of drug, and at the time of progressive disease or treatment discontinuation.
- ^{dd} Mandatory blood sample will be collected prior to drug initiation and is required as an experimental control ONLY if patients consent to optional tumor tissue samples.

Appendix 2 Schedule of Pharmacokinetic, Pharmacodynamic, and Immunogenicity Assessments

Visit	Timepoint	Sample Type
Cycle 1, Day 1	Prior to the infusion	Serum for atezolizumab PK and ATA ^a EDTA plasma and whole blood for PD
	30 (± 10) min after the end of the infusion	Serum for atezolizumab PK
Cycle 1, Day 8	Any time during visit	Serum for atezolizumab PK
Cycle 2, Day 1	Prior to the infusion ^b	Serum for atezolizumab PK and ATA ^a Plasma and whole blood for PD
Cycle 3, Day 1	Prior to the infusion ^b	Serum for atezolizumab PK and ATA ^a Plasma and whole blood for PD
Cycle 4, Day 1	Prior to the infusion ^b	Serum for atezolizumab PK and ATA ^a
	30 (± 10) min after the end of the infusion	Serum for atezolizumab PK
Cycle 8, Day 1	Prior to the infusion ^b	Serum for atezolizumab PK and ATA ^a Plasma and whole blood for PD
Cycle 12, Day 1	Prior to the infusion ^b	Serum for atezolizumab PK and ATA ^a Plasma and whole blood for PD
Day 1 of Cycle 16 and every 8 cycles thereafter	Prior to the infusion ^b	Serum for atezolizumab PK and ATA ^a Plasma and whole blood for PD
Study drug discontinuation visit	Any time during visit	Serum for atezolizumab PK and ATA ^a Plasma and whole blood for PD
At least 90 days (but no more than 150 days) after last dose of study drug	Any time during visit	Serum for atezolizumab PK and ATA ^a Plasma and whole blood for PD

ATA=anti-therapeutic antibody; PD=pharmacodynamic; PK=pharmacokinetic.

^a Serum samples will be split into 2 × 500 µL serum aliquots, one for PK and one for ATA.

^b Blood draws can occur up to 2 days prior to infusion.

Appendix 3

Modified International Neuroblastoma Response Criteria

Below response assessment is modified from the original INRC publication in 1993.

DEFINITION OF MEASURABLE (EVALUABLE) DISEASE ON CT/MRI SCAN

The presence of at least one lesion that can be accurately measured in at least one dimension with the longest diameter at least 20 mm. With a spiral CT scan, lesions must be at least 10 mm. The investigator will identify up to 10 measurable target lesions to be followed for response. Note that bone lesions will be considered as non-target lesions for evaluation of CT/MRI response since they will be evaluated with MIBG scans.

***Malignant Lymph Nodes.** To be considered pathologically enlarged and measurable, a lymph node must be ≥ 15 mm in the short axis when assessed by CT scan (CT scan slice thickness recommended to be ≤ 5 mm). At baseline and in follow-up, only the short axis will be measured and followed. Serial measurements of lesions are to be done with CT or MRI. The same method of assessment used to characterize each identified and reported lesion at baseline should be used during follow-up.*

RESPONSE CRITERIA FOR MEASURABLE DISEASE ON CT/MRI SCAN

The sum of the longest diameter (LD) for all target lesions will be calculated and reported as the disease measurement. The response of the CT/MRI lesions will be defined as outlined below:

- Complete response (CR): Disappearance of all target and non-target CT/MRI lesions
- Very good partial response (VGPR): Greater than 90% decrease of the disease measurement for CT/MRI lesions, taking as reference the disease measurement done to confirm measurable disease at study entry; non-target CT/MRI lesions stable to smaller in size
- Partial response (PR): At least a 30% decrease in the disease measurement for CT/MRI lesions, taking as reference the disease measurement done to confirm measurable disease at study entry; non-target CT/MRI lesions stable to smaller in size
- Progressive disease (PD): At least a 20% increase in the disease measurement, taking as reference the smallest disease measurement since the treatment started, or a new site of tumor; non-target CT/MRI lesions stable, smaller, or increased in size
- Stable disease (SD): Neither sufficient shrinkage to qualify for PR nor sufficient increase to qualify for PD taking as reference the smallest disease measurement since the treatment started; no new sites of disease

Appendix 3

International Neuroblastoma Response Criteria (cont.)

RESPONSE CRITERIA FOR MORPHOLOGIC BONE MARROW DISEASE

Only those patients with morphologic evidence of neuroblastoma by routine H and E staining (NSE staining only is not evaluable) will be evaluable to assess bone marrow response.

- CR: No tumor cells detectable by routine morphology on two subsequent bilateral bone marrow aspirates and biopsies done at least three weeks apart after study entry.
- PD: Tumor seen on morphology on two consecutive bone marrows done at least 3 weeks apart in patients who had no tumor in bone marrow at study entry
Patient may be declared to have PD in bone marrow after only one diagnostic bone marrow at the discretion of the treating physician
Patients who enter study with bone marrow tumor by morphology will be considered to have PD if there is a minimum of 25% tumor in the marrow by morphology and a doubling in the amount of tumor in the marrow compared with the level present at study entry. For example, a patient entering with 5% tumor in marrow by morphology must increase to >25% tumor to have PD; a patient entering with 30% tumor must increase to >60% tumor.
- SD: Persistence of an amount of tumor in the bone marrow by morphology that does not meet criteria for either CR or PD
Patients who clear morphologic tumor but have immunocytologic tumor will be called SD.

RESPONSE CRITERIA FOR MIBG-POSITIVE LESIONS

All patients with known MIBG-avid lesions will be evaluable for MIBG response following the first course of therapy. The following criteria will be used to report MIBG response:

- CR: Complete resolution of all MIBG-positive lesions
- PR: Resolution of at least one MIBG-positive lesion, with persistence of other MIBG positive lesions
- SD: No change in MIBG scan in number of positive lesions (includes patients who have same number of positive lesions but decreased intensity)
- PD: Development of new MIBG-positive lesions

Appendix 3

International Neuroblastoma Response Criteria (cont.)

DEFINITION OF OVERALL RESPONSE FOR EACH PATIENT WITH NEUROBLASTOMA

The International Neuroblastoma Response Criteria were developed to define responses in patients being treated with frontline therapy from diagnosis.¹ These criteria were utilized as a basis for the following response criteria, which integrate response at all sites defined as measurable in this study, including CT/MRI lesions that meet RECIST criteria, MIBG-positive lesions, and bone marrow disease. These criteria will be used to define the overall response for each patient.

- CR: Disappearance of all target lesions; no evidence of tumor at any site (chest, abdomen, liver, bone, bone marrow, nodes, etc.); homovanillic acid (HVA) and vanillylmandelic acid (VMA) normal
- VGPR: Greater than 90% decrease of the disease measurement for CT/MRI target lesions, taking as reference the disease measurement done to confirm measurable disease in target lesions at study entry; all preexisting bone lesions with CR by MIBG; MIBG scan can be \pm or CR in soft tissue lesions corresponding to lesions on CT/MRI; CR in bone marrow; no new sites of tumor; HVA/VMA normal
- PR: At least a 30% decrease in the disease measurement for CT/MRI target lesions, taking as reference the disease measurement done to confirm measurable disease in target lesions at study entry; bone marrow with CR; MIBG with either PR or CR in bone lesions; MIBG may be SD or CR in soft tissue lesions corresponding to lesions on CT/MRI; HVA/VMA may still be elevated.
- PD: Any one of the following:
 - At least a 20% increase in the disease measurement for CT/MRI target lesions, taking as reference the smallest disease measurement recorded since the start of treatment
 - Appearance of one or more new lesions or new sites of tumor
 - PD as defined above for either bone marrow or MIBG lesions
- SD: Stable disease by either CT/MRI lesion, bone marrow, or MIBG criteria; no new lesions; no new sites of disease

The overall response as assessed at any particular timepoint based on the various disease sites is summarized in the table below.

¹ Brodeur GM, Pritchard J, Berthold F, et al. Revisions of the international criteria for neuroblastoma diagnosis, staging, and response to treatment. *J Clin Oncol* 1993;11:1466–77.

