4.5.5 Tumor and Response Evaluations

4.5.5.1 Tumor Assessments

All known sites of disease must be documented at screening and re-assessed at each subsequent tumor evaluation. Baseline tumor assessments should be performed within 28 days prior to initiation of study drug (Day 1 of Cycle 1). Tumor assessments must be performed during the last week of Cycles 2, 4, 6, and 8 and every 4th cycle thereafter (i.e., within 7 days prior to Day 1 of the next cycle). At the investigator's discretion, unscheduled tumor assessments may be performed at any time if progressive disease is suspected. For patients who continue treatment beyond radiographic progressive disease because of possible pseudoprogression, a follow-up scan must be performed after 2 cycles or earlier if clinically indicated.

Response will be assessed by the investigator on the basis of physical examinations, CT scans, MRI scans, fluorodeoxyglucose-positron emission tomography (FDG-PET) scans, or MIBG scans, as appropriate. *Tumor assessment imaging should include all areas of known disease. A chest CT is also required to be performed at each assessment.* An objective response should be confirmed by repeat assessments ≥ 4 weeks after initial documentation. The same *imaging techniques and procedures* used to assess disease sites at screening should be used throughout the study (e.g., the same contrast protocol

for CT scans). To the extent that is feasible, assessments should be performed by the same evaluator to ensure internal consistency across visits.

Patients with neuroblastoma must have a MIBG scan and bilateral bone marrow aspirates and/or biopsies done for disease evaluation. If the enrollment bone marrow aspirates and/or biopsy tissue samples are negative for disease, subsequent bone marrow aspirates and/or biopsy tissue samples are not needed. Patients with evidence of bone marrow disease at screening require bone marrow evaluation with scheduled disease evaluations until they have had two consecutive evaluations that are negative for disease. Patients with neuroblastoma should also have urine catecholamine test results (including homovanillic acid and vanillylmandelic acid) sent at screening and with all responses assessments.

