Appendix 4 Revised Response Criteria for Malignant Lymphoma (cont.)

Timepoint Response

Target Lesions	Non-Target Lesions	New Lesions ^a	Timepoint Response
CR	CR	No	CR
CR	SD	No	PR
CR	UE	No	UE
PR	UE	No	UE
PR	CR	No	PR
PR	SD	No	PR
SD	UE	No	UE
SD	CR	No	SD
SD	SD	No	SD
PD	Any	Yes/No	PD
Any	PD	Yes/No	PD
Any	Any	Yes	PD
UE	Non-PD	No	UE
UE	UE	No	UE
CR	NA ^c	No	CR
PR	NA ^c	No	PR
SD	NA ^c	No	SD
NA ^b	SD	No	SD
NA ^b	CR	No	CR
NA ^b	UE	No	UE
NA ^b	NA ^c	No	UE

CR=complete response; NA=not applicable; PD=progressive disease; PR=partial response; SD=stable disease; UE=unable to evaluate.

Note: Modified from Cheson BD, Pfistner B, Juweid ME, et al. Revised response criteria for malignant lymphoma. J Clin Oncol 2007;25:579–86.

^a Identification of new lesions at a post-baseline time point will result in a response assessment of PD. If an identified new lesion subsequently becomes UE, the timepoint response will be recorded as PD unless the new lesion has proven to have resolved.

^b No target lesions identified at baseline.

^c No non-target lesions identified at baseline.

Appendix 4

Revised Response Criteria for Malignant Lymphoma (cont.)

Response should be determined on the basis of radiographic and clinical evidence of disease. For the end-of-treatment response assessment, an FDG-PET will be performed 6–8 weeks after the last study treatment. Assessment of PET should follow the criteria described by Juweid et al. 2007, which is presented in the table Response Definitions for Clinical Trials.

COMPLETE RESPONSE

- Complete disappearance of all detectable clinical evidence of disease and disease-related symptoms if present before therapy
- Typically ¹⁸F-fluorodeoxyglucose (FDG)–avid lymphoma: in patients with no pre-treatment positron emission tomography (PET) scan or when the PET scan was positive before therapy, a post-treatment residual mass of any size is permitted as long as it is PET negative.
- Variably FDG-avid lymphomas/FDG avidity unknown: in patients without a pre-treatment PET scan, or if a pre-treatment PET scan was negative, all lymph nodes and nodal masses must have regressed on CT to normal size (≤ 1.5 cm in their greatest transverse diameter for nodes > 1.5 cm before therapy). Previously involved nodes that were 1.1 to 1.5 cm in their long axis and > 1.0 cm in their short axis before treatment must have decreased to ≤ 1.0 cm in their short axis after treatment.

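### Appendix 3, read as written, cannot give PR or VGPR to a neuroblastoma patient whose marrow was negative at entry, nor PR to one with no MIBG-avid bone lesions

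*Combined protocol and SAP*

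**What the plan says.** **Overall response, Appendix 3 text.**
- PR needs a CT/MRI decrease of at least 30%, together with "bone marrow with CR; MIBG with either PR or CR in bone lesions"; catecholamines may stay elevated.
- VGPR needs a decrease of more than 90%, "all preexisting bone lesions with CR by MIBG", and "CR in bone marrow; no new sites of tumor; HVA/VMA normal".
- CR needs all target lesions gone, normal catecholamines, and "no evidence of tumor at any site (chest, abdomen, liver, bone, bone marrow, nodes, etc" and so on.

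**Site-level rules, Appendix 3.** Marrow response is evaluable only in patients with morphologic marrow disease. Marrow CR means no tumor cells "on two subsequent bilateral bone marrow aspirates and biopsies done at least three weeks apart after study entry". For MIBG, "All patients with known MIBG-avid lesions will be evaluable for MIBG response"; no category is given for other patients.

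**Table 1 of Appendix 3.** The CR row shows CR in every imaging and marrow column. The VGPR row asks for MIBG CR in bone lesions and marrow CR. The PR row asks for CT/MRI PR, MIBG PR or CR in bone lesions, and marrow CR, with any catecholamine result. No row provides for a site that was never involved.

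**Section 4.5.5.1.** If the enrollment marrow is "negative for disease, subsequent bone marrow aspirates and/or biopsy tissue samples are not needed".

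**Use of the result.** ORR is a primary efficacy endpoint (Section 6.6.1). It counts patients who are determined to have responded, out of all patients who received any study drug (Section 6.6). Table 3 asks for at least 3 responders among a minimum of 10 neuroblastoma patients before expansion.

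**The concern.** Patients with soft-tissue disease on CT/MRI but clear marrow, or without avid bone lesions, are eligible for this cohort. For them the PR definition asks for a response at a site where there was nothing to respond. The gap runs one way. The marrow progression rule expressly covers patients with no marrow tumor at entry, and the progression rows of Table 1 accept any result elsewhere, so such a patient can be scored as progressing but not, on the literal text, as PR. The lymphoma table in Appendix 4 handles the parallel case with not-applicable rows, footnoted for example "No non-target lesions identified at baseline".

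At stake are the neuroblastoma ORR and the expansion decision. Response is judged by investigators at approximately 50 sites, so identical scans could be scored differently.

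**Working it through.** **1. Marrow negative at entry.** PR and VGPR both require marrow CR, in the text and in Table 1. Marrow CR requires morphologic marrow disease at entry and two post-entry bilateral studies. The patient has no such disease, and Section 4.5.5.1 does not call for the later studies. Marrow CR cannot be reached, so neither PR nor VGPR can be assigned.

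**2. No MIBG-avid bone lesion.** PR requires MIBG PR or CR in bone lesions. With no such lesion there is nothing to grade, so PR cannot be assigned.

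**3. Text against table.**

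| Overall response | Text | Table 1 |
|---|---|---|
| CR | No tumor at any site; a never-involved site satisfies this | CR in each of CT/MRI, MIBG and marrow |
| VGPR, MIBG part | Preexisting bone lesions only; met if there were none | CR in bone lesions, no qualification |
| VGPR, marrow part | Marrow CR | Marrow CR |
| PR, CT/MRI part | Any decrease of at least 30% | PR only |

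**4. Every combination without progression, looked up in Table 1.** States: CT/MRI SD, PR, VGPR, CR (4); MIBG SD, PR, CR, not involved (4), with PR and CR read as bone-lesion response; marrow SD, CR, not involved (3); catecholamines normal or elevated (2).
- Marrow not involved: 4 × 4 × 2 = 32 combinations; 32 match no row.
- MIBG not involved: 4 × 3 × 2 = 24 combinations; 24 match no row.
- All sites involved: 4 × 3 × 2 × 2 = 48 combinations; 32 SD, 4 PR, 1 VGPR, 1 CR and 10 with no row.

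Of those 10, six have CT/MRI CR or VGPR with marrow CR. Four of the six have MIBG PR (either catecholamine result), and two have MIBG CR with elevated catecholamines. The PR text covers all six; the PR row does not. The other four have CT/MRI SD with MIBG PR or CR and marrow CR. The SD text covers them, so they do not affect ORR.

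**5. A constructed patient.** A soft-tissue mass shrinks from 60 mm to 30 mm, (30 − 60)/60 = −50%, on two scans 6 weeks apart. Marrow was negative at entry and the MIBG bone response is PR. The shrinkage exceeds 30% and is confirmed, yet no Table 1 row applies and the PR text is not met.

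**6. Illustration on the expansion rule.** From Table 3: n = 10, at least 3 responders, historical rate 18%. The plan states no alpha or power, so there is no figure to reproduce. Assumptions not in the documents: true ORR p; a share q of patients unassignable and all counted as non-responders; the same true response rate inside and outside that group. The observed rate is then p(1 − q), and the chance of meeting the rule is 1 − P(0) − P(1) − P(2) under a binomial with n = 10.
- p = 0.30, q = 0: 1 − 0.0282 − 0.1211 − 0.2335 = 0.617.
- p = 0.30, q = 0.30: rate 0.21; 1 − 0.0947 − 0.2517 − 0.3011 = 0.353 (from unrounded terms).

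| True ORR | q = 0 | 20% | 30% | 50% | 70% |
|---|---|---|---|---|---|
| 18% | 0.263 | 0.164 | 0.122 | 0.054 | 0.014 |
| 30% | 0.617 | 0.444 | 0.353 | 0.180 | 0.054 |
| 40% | 0.833 | 0.669 | 0.562 | 0.322 | 0.109 |
| 50% | 0.945 | 0.833 | 0.738 | 0.474 | 0.180 |

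**The case against.** A reader might infer that these patients are automatically non-responders whatever the tumor does. The documents do not say so. The only explicit non-responder rule in Section 6.6.1 covers patients with no post-baseline assessment; the patients here simply match no row. Nor is every response category closed to them: the CR text can be met by sites that were never involved, and the VGPR text limits its MIBG condition to preexisting bone lesions. Both points stand and limit the claim.

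It can also be argued that the intended reading is plain. Appendix 3 introduces the overall response as combining the sites that are measurable in the study, and a protocol would hardly waive the very marrow study a patient needs in order to respond. That is a fair guide to intent, but it is introductory wording and inference, and the operative definitions and table say otherwise.

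Three further points have weight. The numbers in step 6 rest on an unsourced share and on no responses at all in the affected group, although CR remains open under the text. Missing the Table 3 count does not by itself close the cohort: Section 3.1.2 says enrollment may be stopped, and it allows extension on strong evidence of a positive signal in a slow-enrolling, rare cohort. The secondary irRC analysis has no marrow or MIBG condition for its partial response, so such a response would be visible there, though that does not repair the primary endpoint.

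**Conclusion.** The point holds in this form. As written, Appendix 3 does not allow PR or VGPR when the marrow was negative at entry, nor PR when there are no MIBG-avid bone lesions. The CR and VGPR texts conflict with their Table 1 rows, and the PR row omits six combinations that the PR text covers. The neuroblastoma ORR and the 3-of-10 count therefore depend on an unstated investigator convention. If the literal reading is applied, the bias in ORR is downward, because unassignable patients stay in the denominator.

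The size cannot be computed from the documents. The fall from 0.62 to 0.35 illustrates one assumed case (true ORR 30%, 30% unassignable and all counted as non-responders) and is not an estimate for this trial. The textual finding rests on none of those assumptions. It should be corrected before the neuroblastoma cohort is assessed.

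**What to change.** In the Appendix 3 text and Table 1:
1. State that a component (CT/MRI, MIBG, marrow) with no disease at study entry is recorded as not involved and does not limit the overall response, provided no disease is detected there on the assessments the protocol already requires. For MIBG, say that this applies to bone lesions on their own, so that avid soft-tissue disease alone does not block PR.
2. Align the CR and VGPR rows of Table 1 with the text.
3. Change the CT/MRI entry of the PR row to PR/VGPR/CR, when the CR or VGPR row is not met, and state that rows are applied in the order CR, VGPR, PR. Without that order the wider PR row would overlap the two above it.

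The cost is appendix wording and the matching lines in the response derivation. No new assessments are needed. The proviso in item 1 relies on existing assessments because repeat marrows stay waived for patients with negative marrow at entry.
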